12.3.3	Deaths	55
12.4	Clinical Laboratory Evaluation	56
12.4.1	Hematological Abnormalities.....	56
12.4.2	Biochemical Abnormalities	57
12.4.3	Other Metabolic Parameters	59
12.4.4	Laboratory Values over Time.....	60
12.5	Subgroup Analyses Related to Safety	65
12.6	Concomitant Medication during Treatment	75
12.7	Subsequent Therapy	76
12.8	PRO at treatment	76
13	DB Listings.....	80
14	ICH Listings	87
15	History of Changes	89

ABBREVIATIONS AND GLOSSARY

AE	Adverse Event
ALT (SGPT)	Alanine Aminotransferase
ANC	Absolute Neutrophil Count
AP	Alkaline Phosphatase
AST (SGOT)	Aspartate Aminotransferase
ATC	Anatomical Therapeutic Chemical
BMI	Body Mass Index
BSA	Body Surface Area
CI	Confidence Interval
CPK	Creatine Phosphokinase
CR	Complete Response
CRF	Case Report Form
CT	Computed Tomography
DF	Degrees of Freedom
DNA	Deoxyribonucleic Acid
DR	Duration of Response
ECG	Electrocardiogram
ECOG	Eastern Cooperative Oncology Group
EORTC	European Organization for Research and Treatment of Cancer
EOT	End of Treatment
EPO	Erythropoietin
FU	Follow-up
CSF	Colony Stimulating Factor
HR	Hazard Ratio
IA	Investigator Assessment
IC	Informed Consent
IDMC	Independent Data Monitoring Committee
IORT	Intraoperative Radiation Therapy
IRC	Independent Review Committee
ITT	Intention-to-treat
LR	Log Rank Test
MedDRA	Medical Dictionary for Regulatory Activities
mo	Months
NA	Not Available
NCI-CTCAE	National Cancer Institute Common Terminology Criteria for Adverse Events
NE	Not Evaluable
NOS	Not Otherwise Specified
ORR	Overall Response Rate
OS	Overall Survival
PARPi	Poly(ADP-ribose) Polymerase Inhibitors
PD	Progressive Disease
PLD	Pegylated Liposomal Doxorubicin
PFS	Progression Free Survival
PR	Partial Response
PRO	Patient-Reported Outcomes
PS	Performance Status
PT	Preferred Term

RECIST	Response Evaluation Criteria In Solid Tumors
SAE	Serious Adverse Event
SD	Stable Disease
SOC	System Organ Class
STD	Standard Deviation
UK	Unknown
USA	United States of America
vs.	versus
WBC	White Blood Cells
WHO	World Health Organization

1 STUDY RATIONALE

Patients with relapsed platinum-resistant ovarian cancer have poor prognosis. New treatment options are needed to treat these patients, particularly agents with novel mechanisms of action.

PM01183 is a new chemical entity that induces double-strand DNA breaks through binding to the DNA minor groove. PM01183 has *in vitro* and *in vivo* anticancer activity in several platinum sensitive and resistant ovarian cancer-derived cell lines.

On the basis of preclinical results, a controlled, phase II exploratory clinical trial including a randomized stage was conducted to evaluate the activity and safety of PM01183 as a single agent in platinum-resistant/refractory advanced ovarian cancer (PM1183-B-002-11). The primary endpoint of the study was the overall response rate (ORR). The global endpoint was met, and the results of the randomized second stage of the study showed PM01183 more active than topotecan in this indication.

Therefore, a randomized trial has been proposed to compare lurtotecan (PM01183) vs. pegylated liposomal doxorubicin (PLD) or topotecan in advanced ovarian cancer patients with platinum-resistant disease.

A full rationale for the study may be found in the appropriate sections of the study Clinical Protocol.

2 OVERALL STUDY DESIGN

Multicenter, open-label, randomized, controlled phase III clinical trial to evaluate the activity and safety of PM01183 vs. PLD or topotecan as control arm in patients with platinum-resistant ovarian cancer.

A single-agent PM01183 dose will be explored in the experimental arm (Arm A) vs. PLD or topotecan in the control arm (Arm B).

Central randomization will be implemented in all patients who fulfill the inclusion criteria; patients will be assigned to each treatment arm at a 1:1 ratio. If the patient had not previously received PLD or topotecan, the assigned treatment in case the patient is randomized to the control arm (Arm B) will be based on the reported Investigator's preference with regard to each of these two drugs. However, if the number of patients randomized to either PLD or topotecan reaches 60% of the total number of patients expected in the control arm (i.e., 126 patients), then the treatment of choice in the control arm will be restricted to the less frequent control drug until the end of accrual. Once the 60% is achieved for one of the two control agents, the patient will not be eligible for this trial if this agent is the only possible option (e.g., if the patient has been previously treated with topotecan, then PLD is the only possible option if the patient is randomized to Arm B and the patient will not be eligible if an accrual of 60% has been reached for PLD). Stratification will be performed according to Eastern Cooperative Oncology Group (ECOG) performance status (PS) (0 vs. ≥ 1), prior platinum-free interval (1-3 months vs. >3 months) (Platinum Free Interval = PFI: time elapsed between completion of the last platinum-containing regimen and the subsequent relapse or progression) and prior chemotherapy (1-2 vs. 3 lines).

Up to 420 patients with platinum resistant ovarian cancer (disease relapse or progression within one to six months after last platinum-containing chemotherapy) will be included in the trial.

An Independent Data Monitoring Committee (IDMC) will oversee the conduct of the study. Operational details for the IDMC will be detailed in the corresponding charter.

[figure not shown]
An Independent Review Committee (IRC) will determine the best patient's response and assign the date of objective response or progression/censoring according to Response Evaluation Criteria In Solid Tumors (RECIST) v.1.1. Operational details for the IRC, the algorithm and its validation by an expert panel is described in detail in the IRC charter.

An interim safety analysis will be performed in the PM01183 arm only (Arm A) when 40 patients are enrolled in this arm. Based on the results of this analysis, the IDMC may provide recommendations on the primary prophylactic use of colony stimulating factors (CSFs) as part of the therapy in the experimental Arm A. The recruitment in both treatment arms will not be stopped during the conduct of the interim safety analysis.

A futility analysis will be performed when 210 patients are recruited. The recruitment will not be put on hold. The IDMC will review efficacy and safety data available at that time and, based on the observed results, might recommend stopping the trial; no claim for efficacy in comparison with the control arm will be made at this analysis.

Crossover after treatment discontinuation from the control Arm B to the experimental Arm A is not allowed.

A summary of the study design is shown in the below figure.

*If the patient had not previously received PLD or topotecan, the assigned treatment in case that the patient is randomized to the control arm (Arm B) will be based on the reported Investigator's preference with regard to each one of these two drugs. However, if the number of patients randomized to either PLD or topotecan reaches the 60% of the total number of patients expected in the control arm (i.e., 126 patients), then the treatment of choice in the control arm will be restricted to the less frequent control drug until the end of accrual.

Patients will receive the study treatment while it is considered to be in their best interest. Specifically, treatment will continue until disease progression, unacceptable toxicity, intercurrent illness of sufficient magnitude to preclude safe continuation of the study, Investigator's decision, patient refusal, non-compliance with the study requirements, a major protocol deviation that may affect the risk/benefit ratio for the participating patient, or requirement of > two dose reductions.

All adverse events (AEs) will be graded according to the National Cancer Institute Common Terminology Criteria for Adverse Events (NCI-CTCAE) v.4. Treatment delays, dose reduction requirements and reason for treatment discontinuation will be monitored throughout the study. The safety profile of patients will be monitored throughout the treatment and up to 30 days after the last treatment infusion (end of treatment, EOT), until the patient starts a new antitumor therapy or until the date of death, whichever occurs first. Any treatment-related AEs will be followed until recovery to at least grade 1 or stabilization of symptoms, whichever occurs first.

Patients will be evaluated at scheduled visits on three study periods: Pre-treatment, Treatment and Follow-up. This clinical trial will finish (clinical cutoff) 24 months after randomization of the last patient.

3 PATIENTS EVALUABILITY CRITERIA

Patients must fulfill all the inclusion/exclusion criteria to be eligible to participate in the study. Randomized patients will not be replaced.

3.1 Intention-to-Treat (ITT) Population

All patients randomized to either treatment arm independent of whether they received study drug or not, and analyzed in the group where they were allocated.

3.2 Safety Population

Safety population or “all treated patients” population will be defined as patients who have received at least part of one infusion of the investigational agents, and analyzed in the group where they were treated.

4 OBJECTIVES AND ENDPOINTS

4.1 Primary Objective

- To determine a difference in progression-free survival (PFS) between lurbinectedin (PM01183) and PLD or topotecan in platinum-resistant ovarian cancer patients according to RECIST v.1.1.

4.2 Secondary Objectives

To evaluate:

- Overall survival (OS).
- Antitumor activity.
- Safety profile.
- Patient-reported outcomes (PRO).
- To characterize the plasma pharmacokinetics (PK) of PM01183 using a sparse sampling scheme in the PM01183 treatment arm (Arm A).
- Subgroup analyses of the PM01183 arm vs. PLD or topotecan.

- To conduct an exploratory pharmacogenetic and pharmacogenomic (PGx) sub-study.

4.3 *Endpoints*

Primary endpoint:

- **Progression-free survival (PFS) by IRC** is defined as the time from the date of randomization to the date of documented progression per RECIST v.1.1 or death (regardless of the cause of death). If the patient receives further antitumor therapy or is lost to follow-up before PD, PFS will be censored at the date of last tumor assessment before the date of subsequent antitumor treatment.

Secondary endpoints:

- **Progression-free survival (PFS) per RECIST v.1.1 by Investigator's Assessment (IA).**
- **Overall survival (OS)** will be calculated from the date of randomization to the date of death (death event) or last contact (in this case, survival will be censored on that date).
- **Landmark analyses:**
 - **PFS at 6 and 12 months by IRC/IA** will be the Kaplan-Meier estimates of the probability of being free from progression (per RECIST v.1.1) and death at these time points.
 - **OS at 12 and 24 months** will be the Kaplan-Meier estimates of the probability of being alive at these time points.
- **Best antitumor response by IRC/IA** will be the best response obtained in any evaluation according to the RECIST v.1.1. before progressive disease. Irrespectively of treatment arm, radiological and clinical tumor assessment will be performed symmetrically at baseline and every eight weeks from randomization until evidence of PD. Patients who finish treatment without PD will continue with the tumor assessments every eight weeks (\pm two weeks) from randomization until PD, start of a new antitumor therapy, death or date of study termination (clinical cut-off), whichever occurs first.
- **Duration of response (DR) by IRC/IA** will be calculated from the date of first documentation of response per RECIST v.1.1 (complete or partial response, whichever comes first) to the date of documented PD or death. The censoring rules defined above for PFS will be used for duration of response.
- **Best response according to tumor marker evaluation (CA-125)** will be the best response obtained according to GCIG criteria. Irrespectively of treatment arm, tumor marker assessment will be performed symmetrically at baseline and every eight weeks from randomization until evidence of PD.
- **Treatment safety profile:** AEs, serious adverse events (SAEs) and laboratory abnormalities will be coded by the Medical Dictionary for Regulatory Activities (MedDRA), graded according to the NCI-CTCAE v. 4 and analyzed. Dose reductions or delays required due to treatment-related AEs, and reasons for treatment discontinuations will be also assessed.
- **Patient-reported outcomes (PRO):** To measure the quality of life of patients, EORTC QLQ-C30 and EORTC QLQ-OV28 questionnaires will be completed by the patients every eight weeks in all three treatment arms.

- **Plasma pharmacokinetics (PK) of PM01183** will be evaluated using a sparse sampling scheme in the PM01183 treatment arm (Arm A). Details will be given in a population PK analysis plan and the results of the population PK analysis will be presented in a separate report.
- **Subgroup analyses:** Subgroup analyses of the PM01183 arm *vs.* PLD or topotecan outcomes will be performed.
- **Pharmacogenetics:** This analysis will be performed in those patients who signed the IC for the PGx sub-study. The presence or absence of known polymorphisms from a single sample collected just before the PM01183 treatment start will be assessed to explain the individual variability in the main PK parameters.
- **Pharmacogenomics:** This exploratory analysis will be performed in those patients treated in any arm who signed the IC for the PGx sub-study. Samples from Arm B will be used as controls in order to differentiate between the prognostic or predictive value of any obtained finding. mRNA or protein expression levels of factors involved in DNA repair mechanisms, or related to the mechanism of action of PM01183 or to the pathogenesis of the disease, will be evaluated from prior available tumor tissue samples obtained at diagnosis or relapse. Their mutational status might also be analyzed. Their correlation with the clinical response and outcome after treatment will be assessed.

5 SAMPLE CONSIDERATIONS

5.1 Randomization and Stratification

Central randomization will be implemented in all patients who fulfill the eligibility criteria. Randomization of patients should occur as close in time as possible to the administration of the first dose of study drug. Patients will be assigned to each treatment arm (Arm A or Arm B) at a 1:1 ratio. If the patient had not previously received PLD or topotecan, the assigned treatment in case that the patient is randomized to the control arm (Arm B) will be based on the reported Investigator's preference with regard to each one of these two drugs. However, if the number of patients randomized to either PLD or topotecan reaches the 60% of the total number of patients expected in the control arm (i.e., 126 patients), then the treatment of choice in the control arm will be restricted to the less frequent control drug until the end of accrual. Stratification will be performed according to ECOG PS (0 *vs.* ≥ 1), prior platinum-free interval [PFI] (1-3 months *vs.* >3 months) and prior chemotherapy (1-2 *vs.* 3 lines).

5.2 Sample Size

This phase III clinical trial is designed to determine a statistically significant difference in PFS by IRC between PM01183 and a control arm with PLD or topotecan in ovarian cancer patients with platinum-resistant disease.

Patients will be randomized to receive PM01183 given as 3.2 mg/m² (Arm A) or either topotecan or PLD (Arm B).

The prospective assumptions are a 30% reduction in the relative risk of progression or death (HR=0.7) to be achieved with the experimental arm (PM01183), at a one-sided 2.5% significance level with at least 90% power, following exponential distributions and fulfilling the proportional hazard assumption. Median PFS with control arm is expected to be around 3.5 months. It is forecasted that an observed HR of approximately 0.8 will have enough power to reject the null hypothesis (HR=1).

Approximately 420 patients with platinum resistant ovarian cancer will be necessary to stratify and randomize at a 1:1 ratio over 18 months (~23 patients/month). The required 332 PFS events are expected to occur around six months after randomization of the last patient. Therefore, the IDMC meeting after the IRC review to test PFS is expected to occur about one year after randomization of the last patient.

With the prospective assumptions above mentioned, about 175 PFS events are expected in the control arm and 157 in the PM01183 treatment arm.

The IDMC will review the results of the analyses. The IRC will determine the patient's best response and assign the date of objective response or progression/censoring according to the RECIST v.1.1.

5.2.1 *Futility Analysis*

A futility analysis will be performed when 210 patients are recruited (i.e., ~105 patients enrolled in each arm). The recruitment will not be put on hold.

In the futility analysis, the sponsor will make no claim of efficacy, consequently this futility analysis and the final analysis to reject the null hypothesis ($HR=1$) are planned; the significance level will be determined by the actual number of observed events by IR. To maintain scientific integrity, type II error will be controlled by a spending function defined by O'Brien-Fleming boundaries. Following the prospective assumptions, the interim analysis will occur at less than one year after start of recruitment. At this moment, with the available information collected after balancing efficacy and safety, the IDMC might recommend stopping the trial.

The IDMC may request to review other preliminary safety/efficacy parameters, but no claim of superiority will be done; therefore, no type I/II error corrections will be applied.

5.2.2 *Interim Safety Analysis*

An interim safety analysis, performed when 40 patients are enrolled in Arm A, will test if the addition of primary CSF prophylaxis might be necessary in this arm. With the information available at that time, a Bayesian test assuming non-informative prior distribution will be done to assess the null hypothesis of febrile neutropenia $\leq 20\%$ vs. the alternative hypothesis of febrile neutropenia $>20\%$. If the probability associated with the alternative hypothesis is higher than 50% (e.g., 8 cases out of 40 patients), the addition of primary CSF prophylaxis will be considered necessary.

At the time of the interim safety analysis, recruitment in Arm B (PLD or topotecan) is also expected to be approximately 40 patients.

The IDMC may request to review other preliminary safety/efficacy parameters, but no claim of superiority will be done; therefore, no type I/II error corrections will be applied.

6 STATISTICAL METHODOLOGY FOR EFFICACY

6.1 *Efficacy Definitions*

Primary endpoint.

Progression-free survival (PFS) by IRC is defined as the time from the date of randomization to the date of documented progression per RECIST v.1.1 or death (regardless of the cause of death). If the patient receives further antitumor therapy or is

lost to follow-up before PD, PFS will be censored at the date of last tumor assessment before the date of subsequent antitumor treatment.

Irrespectively of treatment arm, radiological and clinical tumor assessment will be performed symmetrically at baseline and every eight weeks from randomization until evidence of PD is found. Patients who finish treatment without radiological PD will continue with the tumor assessments every eight weeks (\pm two weeks) from randomization until PD, start of a new antitumor therapy, death or date of study termination (clinical cut-off), whichever occurs first.

After radiological PD is documented or a new antitumor therapy is started, patients will be followed for survival at least every three months (\pm two weeks) from the end-of-treatment visit until death or date of study termination, whichever occurs first. Once the whole recruitment is completed, the 3-month follow-up for patients who discontinue treatment due to PD will be performed according to calendar time. Follow-up for survival, after radiological PD is documented or new therapy is started, may be made by telephone calls to the investigational sites.

The date of clinical and/or radiological PD and the date of death will be registered and documented as appropriate.

Copies of CT scans, MRIs and any other documented means to evaluate tumor response or progression should be available for external radiological review by an IRC. The IRC will determine the patient's best response, and assign the date of objective response or progression/censoring according to RECIST v.1.1.

Crossover after treatment discontinuation from Arm B to Arm A is not allowed.

Secondary endpoints.

Progression-free survival (PFS) by IA will be calculated using the same methodology as explained above for IRC assessment but following investigator assessments.

Overall survival (OS) is defined as the time from the date of randomization to the date of death (death event) or last contact (in this case, survival will be censored on that date). If applicable and more than one OS analysis is performed type I error will be controlled by spending function defined by O'Brien-Fleming boundaries. Counting out subsequent therapies impact, sample size is powered to detect OS differences in the 20-30% range. Final OS analysis is planned 24 months after randomization of last patient (planned end of study date).

Landmark analyses of PFS at 6/12 months by IRC/IA and OS at 12/24 months will be the Kaplan-Meier estimates of the probability of being free from progression and/or alive at these time points.

Best antitumor response by IRC/IA will be the best response obtained in any evaluation according to RECIST v.1.1.

Radiological antitumor activity will be assessed using the RECIST v. 1.1 on a set of measurable lesions identified at baseline as target lesions, and/or non-measurable lesions (if any) identified at baseline as non-target lesions and followed until disease progression (PD) by the appropriate method [computed tomography (CT) scan or magnetic resonance imaging (MRI)].

Duration of response (DR) will be calculated from the date of first documentation of response (complete or partial response, whichever comes first) to the date of documented PD or death. The censoring rules defined above for PFS will be used for duration of response.

Assessments must be done consistently in both treatment arms to ensure a symmetrical assessment of tumor response and progression. Every effort should be made to ensure

that these assessments are done on the required date. Time to n^{th} (i.e. 1, 2, 3...) disease assessment is defined as weeks between randomization and the recorded date of the n^{th} radiology assessment after randomization.

Best response according to tumor marker evaluation (CA-125) will be the best response obtained according to GCIG criteria⁽¹⁾. Irrespectively of treatment arm, tumor marker assessment will be performed symmetrically at baseline and every eight weeks from randomization until evidence of PD.

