All adverse events (AEs) will be graded according to the National Cancer Institute Common Terminology Criteria for Adverse Events (NCI-CTCAE) v.4. Treatment delays, dose reduction requirements and reason for treatment discontinuation will be monitored throughout the study. The safety profile of patients will be monitored throughout the treatment and up to 30 days after the last treatment infusion (end of treatment, EOT), until the patient starts a new antitumor therapy or until the date of death, whichever occurs first. Any treatment-related AEs will be followed until recovery to at least grade 1 or stabilization of symptoms, whichever occurs first.

Patients will be evaluated at scheduled visits on three study periods: Pre-treatment, Treatment and Follow-up (see Section [5.2](#)). This clinical trial will finish (clinical cutoff) when all required OS events have occurred according to statistical assumptions.

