5. PLAN OF THE STUDY

5.1 PLANNED TRIAL PERIODS (FOR THE WHOLE STUDY)

The total duration of the study will be approximately 42 months, including approximately a 18-month enrolment period.

Planned start date (first patient on study): approximately first quarter 2015.

Planned enrolment period: approximately 18 months.

Planned end-of-study date (clinical cutoff): 24 months after randomization of the last patient.

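### The SAP says the trial is powered for OS differences of 20-30%, but for a 20% reduction power is about 52-59%, and only 63% if all 420 patients die

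*SAP*

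**What the plan says.** The OS paragraph of SAP section 6.1 says that, leaving aside subsequent therapy, the "sample size is powered to detect OS differences in the 20-30% range". It places the final OS analysis 24 months after the last patient is randomised and foresees O'Brien-Fleming spending if OS is analysed more than once. It gives no OS power level, alpha, death count or control median.

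The only sizing calculation in either document is for PFS (SAP section 5.2, Protocol section 8.1). It assumes a hazard ratio of 0.70 "at a one-sided 2.5% significance level with at least 90% power", with 332 PFS events. On enrolment, "Approximately 420 patients with platinum resistant ovarian cancer will be necessary to stratify and randomize at a 1:1 ratio over 18 months".

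On when the trial ends, Protocol section 3 says: "This clinical trial will finish (clinical cutoff) when all required OS events have occurred according to statistical assumptions". Protocol section 5.1 says: "Planned end-of-study date (clinical cutoff): 24 months after randomization of the last patient". The Protocol synopsis, Protocol section 5.9, and SAP sections 2 and 6.1 all give the 24-month date.

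**The concern.** The number of patients was set by PFS at a hazard ratio of 0.70. Required events rise as the inverse square of the log hazard ratio, so moving from 0.70 to 0.80 multiplies them by (0.3567/0.2231)² = 2.56. A trial sized for the first cannot also be powered for the second unless it has many more events, and here the number of deaths cannot exceed 420.

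OS is the first-listed secondary objective and has its own stratified log-rank test. A reader who trusts the SAP sentence would take a non-significant OS result as evidence against a 20% reduction in mortality. At the planned cutoff the trial would miss that effect 41-48% of the time.

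The sentence in Protocol section 3 adds a second difficulty. It makes the end of the trial depend on an OS event count that is defined nowhere, in conflict with a fixed calendar cutoff stated elsewhere.

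**Working it through.** **Inputs from the documents.** 420 patients, 1:1, 18 months of accrual (SAP 5.1 and 5.2). Final OS analysis 24 months after the last randomisation, so 42 months from the start (SAP 6.1). One-sided alpha of 2.5%, stated for PFS and assumed here for OS because no OS alpha is given.

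**Assumptions.** The 20-30% range is read as a hazard reduction, the scale used for PFS, so HR 0.80 to 0.70. Control median OS is not a stated design parameter. I use 8.3 months (phase II platinum-resistant controls, Protocol 1.3.1) to 13.3 months (chemotherapy arm of the bevacizumab trial in Protocol section 1.1, Table 1, which excluded refractory patients). Survival is exponential, accrual uniform, and there are no losses.

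**Formulas.** With D deaths in total and 1:1 allocation (Schoenfeld):

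- deaths needed = 4(1.960 + z_power)² / (ln HR)²
- power = Φ(½√D·|ln HR| − 1.960)
- probability of death by cutoff at hazard λ = 1 − (e^(−24λ) − e^(−42λ)) / (18λ)

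**Step 1: reproduce the plan's own figure.** For PFS at HR 0.70 and 90% power: 4(1.960 + 1.282)²/(0.3567)² = 331 events, against the stated 332. With 332 events power is 90.1%. The method matches the plan's.

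**Step 2: deaths needed for OS at HR 0.80.** |ln 0.80| = 0.2231.

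- 80% power: 4(1.960 + 0.842)²/(0.2231)² = 631
- 90% power: 4(1.960 + 1.282)²/(0.2231)² = 845

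Both exceed 420.

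**Step 3: ceiling.** If all 420 die: ½√420 × 0.2231 = 2.287, and Φ(2.287 − 1.960) = 62.8%. The Freedman form gives 62.4%. No survival assumption enters this figure.

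**Step 4: power at the planned cutoff.** For example, a control median of 11 months and HR 0.80 give 210 × 0.868 = 182 control deaths and 210 × 0.804 = 169 experimental deaths, 351 in all, and power 55%. Across the range of medians:

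| True OS HR | Deaths, control median 13.3 to 8.3 months | Power |
|---|---|---|
| 0.80 | 327 to 381 | 52% to 59% |
| 0.75 | 322 to 377 | 73% to 80% |
| 0.70 | 317 to 373 | 89% to 93% |

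The smallest reduction with 80% power is about 25-27% at 327-381 deaths, and 24% with all 420 dead.

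**Step 5: other inputs at HR 0.80.** A control median of 14.2 months (PLD, also in Table 1) gives 318 deaths and 51%. Losing 10% of the deaths gives 48-54%. A one-sided 5% test with all 420 dead gives 74%.

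**Step 6: another reading of the range.** If 20-30% means a gain in median survival (HR 1/1.2 = 0.83 to 1/1.3 = 0.77), power at an 11-month control median is about 40% to 69%, and with all 420 dead 46% to 77%. Neither end reaches 80%.

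**The case against.** The best defence is that the sentence uses power loosely. SAP section 5.2 does so for PFS, where it attaches enough power to an observed HR of about 0.8. With 332 events the just-significant observed HR is exp(−2 × 1.960/√332) = 0.806, so that remark describes a significance threshold. For OS with 327-381 deaths the threshold is 0.805-0.818, and an observed 20-30% reduction would indeed be significant. This may well be where the wording came from. But a sample size powered to detect a difference is understood to refer to a true effect, and when the true effect lies at the threshold, power is only about 50%. The reading explains the sentence without making it correct.

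The SAP's proviso about subsequent therapies does not help either, because the calculation above already assumes no dilution from later treatment.

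Three points on that side do stand. OS is secondary, and the sentence sets no sample size, boundary or analysis date. The planned OS table reports the hazard ratio with a 95% confidence interval, which would show the imprecision to a careful reader. And the Protocol section 3 sentence is a separate matter from the power arithmetic; SAP section 2, which otherwise follows that section closely, already has the 24-month rule in its place.

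**Conclusion.** The OS power statement is wrong as written for the lower part of its range. For a 20% hazard reduction, power cannot exceed about 63%; that ceiling rests only on 420 patients, 1:1 allocation and one-sided 2.5%. The 52-59% at the planned cutoff also rests on control medians of 13.3 to 8.3 months, exponential survival, uniform accrual and no losses. These medians are background data rather than design assumptions, but no value in the range tried brings power near 80%. The 30% end is adequately powered. The defect covers reductions below roughly 25%.

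The event-driven ending in Protocol section 3 conflicts with the 24-month cutoff stated elsewhere and cannot be carried out, since no required number of OS events exists. The PFS sample size, event target and primary analysis are unaffected.

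**What to change.** In SAP section 6.1, replace the sentence with the actual property and its assumptions. For example: for a control median OS of 8.3 to 13.3 months, exponential survival, 18 months of uniform accrual, cutoff 24 months after the last randomisation, no losses and a one-sided 2.5% test, expected deaths and power are 317-373 and 89-93% at HR 0.70, 322-377 and 73-80% at HR 0.75, and 327-381 and 52-59% at HR 0.80. If the sponsor has its own design median for OS, it should state that value and recompute. If it prefers a shorter text, it can limit the claim to the effects that are powered. Either way the OS alpha should be stated.

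In Protocol section 3, replace the sentence on required OS events with the 24-month cutoff used elsewhere.

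The cost is wording in two documents, with no extra patients or follow-up. The stated sensitivity for OS becomes less favourable.
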